14.5 Pharmacokinetic and Pharmacodynamic Analysis

14.5.1 Pharmacokinetic Analysis

Summary statistics will be tabulated for PK parameters by dose. Geometric means and percent coefficients of variation may be reported for C_{max} , AUC_{tau} , and C_{trough} ; arithmetic means and standard deviations may be reported for $t_{1/2}$, CL, and V_{ss} ; and medians, minimum, and maximum may be reported for T_{max} . Population PK analyses may be conducted using data from this study alone or combined with data from other sponsor-conducted studies.

14.5.2 Immunogenicity Analysis

The proportions of participants negative for ADA at baseline with a positive ADA result on study, negative at baseline and remain negative, and positive ADA at baseline that increases or decreases in titer on study will be summarized. Samples with a positive ADA result may be evaluated for further immunogenicity including but not limited to neutralizing capacity. The incidence of neutralizing antibodies may be summarized if available.

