3.2 Secondary Objectives

Secondary Objective	Outcome or Endpoint
Assess PK and immunogenicity (ADA) of MGD020	1. Serum MGD020 concentrations 2. Summary PK parameters for MGD020 3. Incidence of ADA to MGD020
Assess PK and immunogenicity (ADA) of MGD014	1. Serum MGD014 concentrations 2. Summary PK parameters for MGD014 3. Incidence of ADA to MGD014
Assess serum cytokine levels	1. Serum cytokine concentrations

Abbreviations: ADA: anti-drug antibody; PK: pharmacokinetics.

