4 STUDY DESIGN

4.1 Overall Study Design

Study CP-MGD020-01 is a phase 1, open-label, dose-escalation, and multi-dose expansion study of MGD020 as a single agent or in combination with MGD014 in PWH on ART. The study is designed to characterize the safety, tolerability, PK, immunogenicity, and PD of the study drugs. The study consists of 3 parts (Part 1A, Part 1B, and Part 2). In all parts, the participant's standard of care ART regimen is continued throughout the study period.

Part 1A evaluates single ascending doses of MGD020, Part 1B evaluates single ascending doses of MGD020 in combination with fixed-dose MGD014, and Part 2 is a multi-dose expansion cohort with sequential administration of combination MGD020 and MGD014 Q2W for 3 combination doses over 4 weeks.

The study consists of a screening phase of up to 8 weeks, and an approximately 6-week (Part 1A and Part 1B) or 11-week (Part 2) study period (dosing and follow-up), which concludes with an end of study visit (EOSV) approximately 6 weeks (Part 1A and Part 1B) or 7 weeks (Part 2) after the last dose of study drug. Thus, the total study duration for each participant is approximately 14 weeks (Part 1A and Part 1B) or 19 weeks (Part 2). If a participant is unable to complete the study, but has not withdrawn consent, the EOSV is conducted 30 days (+3 day window) after the last dose of study drug.

An independent safety monitor will provide study oversight and evaluate cumulative safety and other clinical data at regular intervals as described in [Section 14.9](#).

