4.1.2 Part 1B: Single Ascending Dose of MGD020 and Fixed-Dose of MGD014

Part 1B commences only after the MTD or MAD of single-agent MGD020 has been determined in Part 1A. During Part 1B, participants will be enrolled and treated with a single ascending dose of MGD020 in combination with a fixed dose of 300 mcg/kg MGD014.

MGD020 and MGD014 will be administered at the doses shown in **Table 2** using a 3+3 design, beginning with Cohort 1, with at least 72 hours between dosing of each participant within a cohort. The first cohort will be treated with a single dose of MGD020 at a dose determined to be one dose level lower than the MTD/MAD from Part 1A (i.e., one dose level lower than MTD_{1A}/MAD_{1A}). MGD014 is dosed at 300 mcg/kg, as determined from Study CP-MGD014-01.

In Part 1A, the MGD020 dose is increased in half-log increments from 1 to a maximum of 300 mcg/kg. In Part 1B, the maximum starting dose of MGD020 for Cohort 1 of Part 1B will thus be 100 mcg/kg (one dose level below the Cohort 6 dose of 300 mcg/kg). In combination with MGD014 at 300 mcg/kg, this would yield a maximum total DART dose of 400 mcg/kg for Cohort 1 of Part 1B, which is less than a half-log increment over the total DART dose that would have been tolerated in Part 1A.

Escalation to the next cohort follows the rules described in **Section 4.2**.

Table 2 MGD020 and MGD014 Combination Dose Escalation Scheme (Part 1B)

Cohort	MGD020 ^a (mcg/kg)	MGD014 (mcg/kg)	Design
-1 ^b	MGD020 MTD _{1A} /MAD _{1A} -2	300	3+3
1	MGD020 MTD _{1A} /MAD _{1A} -1	300	3+3
2	MGD020 MTD _{1A} /MAD _{1A}	300	3+3

- a Dosing for Part 1B will begin with Cohort 1. The MGD020 dose in Cohort 1 will be one dose level below the single-agent MTD/MAD in Part 1A. For example, if the MTD/MAD in Part 1A for MGD020 is 300 mcg/kg, Cohort 1 of Part 1B would receive 100 mcg/kg MGD020 + 300 mcg/kg MGD014.
- b If the dose level in Part 1B Cohort 1 exceeds the MTD, de-escalation to Cohort -1 may be considered. For example, if MTD is exceeded when the Part 1B Cohort 1 dose is 100 mcg/kg MGD020 + 300 mcg/kg MGD014, Cohort -1 of Part 1B would receive 30 mcg/kg MGD020 (MTD_{1A}/MAD_{1A} -2 dose from Part 1A) + 300 mcg/kg MGD014.

Participants who completed Part 1A may be considered for enrollment in Part 1B, provided they meet all eligibility criteria, did not experience DLT in Part 1A, and do not have detectable ADA against MGD014 and/or MGD020 at the completion of Part 1A.

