9.3 Screening Period

The first dose of study drug(s) may be administered within 8 weeks of signing the informed consent. This period is defined as the screening period. Participants will enter the study upon signing the informed consent document. No screening activities outside of usual standard of care will be performed prior to obtaining informed consent.

Participants who sign the informed consent form but fail to meet the eligibility criteria are defined as screen failures. Demographic information, reason for screen failure, and serious adverse events (SAEs) related to study procedures must be recorded on the eCRF.

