b For participants who have been previously exposed to MGD014 or MGD020, obtain screening samples for ADA (MGD014 and MGD020) at least 21 days prior to enrollment to allow for results to be reported before enrollment.

c PK, ADA and cytokine samples may be obtained selectively at additional time points in participants who experience signs and symptoms of IRR or CRS.

Abbreviations: ADA: anti-drug antibody; CRS: cytokine release syndrome; EOI: end of infusion; EOS: end of study; HLA: human leukocyte antigen; IPDA: intact proviral DNA assay; IRR: infusion related reaction; N/A: not applicable; PBMC: peripheral blood mononuclear cell; PD: pharmacodynamic; PK: pharmacokinetic.

Table 11 Pharmacokinetic, Immunogenicity, and Pharmacodynamic Sampling Schedule: Part 2

Study Day	Time Point	Window	PK ^a (Serum)		ADA (Serum)		Cytokines (Serum)	PD: T-cell Binding & Phenotype (Whole Blood)	PD: IPDA & rca- RNA (PBMCs)	HLA Typing (Whole Blood)	PD: QVOA (Leuka- pheresis)	PD: SCA (Plasma)
			MGD020	MGD014	MGD020	MGD014						
-56 to -1	Screening	N/A			X ^b	X ^b					X ^c	
1	Pre-MGD020 infusion	N/A	X	X			X	X	X	X		X
1	EOI MGD020	+ 10 min	X									
1	EOI MGD014	+ 10 min		X								
1	1 h after EOI MGD014	± 5 min	X	X			X	X				
1	4 h after EOI MGD014	± 5 min	X	X			X	X				
2	No specific time	N/A	X	X			X	X				
4	No specific time	N/A	X	X								
8	No specific time	± 1 day	X	X			X	X				
15	Pre-MGD020 infusion	N/A	X	X	X	X	X	X				
15	EOI MGD020	+ 10 min	X									
15	EOI MGD014	+ 10 min		X								
15	4 h after EOI MGD014	± 5 min	X	X			X	X				
29	Pre-MGD020 infusion	N/A	X	X	X	X	X	X				
29	EOI MGD020	+ 10 min	X									
29	EOI MGD014	+ 10 min		X								
29	4 h after EOI MGD014	± 5 min	X	X			X	X				
43	No specific time	± 2 days	X	X					X		X ^c	X
50	No specific time	± 2 days	X	X								
64	No specific time	± 3 days	X	X								
IRR-CRS ^d	No specific time ^d	N/A	X	X	X	X	X					
78/EOS	EOS	± 3 days	X	X	X	X						X

a Obtain pre-infusion PK samples before start of infusion on visit day (dosing day) or day before. When collecting multiple samples, collect PK sample first.

b For participants who have been previously exposed to MGD014 or MGD020, obtain screening samples for ADA (MGD014 and MGD020) at least 21 days prior to enrollment to allow for results to be reported before enrollment.

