4.11 Immunogenicity Endpoints and Analyses

The proportion of participants who are negative for ADA at baseline with a positive ADA result on study, negative at baseline and remain negative, and positive ADA at baseline that increases or decreases in titer on study will be summarized. Samples with a positive ADA result may be evaluated for further immunogenicity including but not limited to neutralizing capacity. The incidence of neutralizing antibodies may be summarized if available. The impact of immunogenicity on safety, PK, and PD may be summarized and explored graphically.

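### In previously exposed participants, baseline ADA rests on a screening sample taken weeks before dosing, so a conversion before Day 1 would be tabulated as an on-study conversion

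*Protocol*

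**What the plan says.** ADA incidence to each drug is a secondary endpoint (Protocol 3.2, for example "Incidence of ADA to MGD020"). Protocol 14.5.2 reports "The proportions of participants negative for ADA at baseline with a positive ADA result on study", alongside those who stay negative and those positive at baseline whose titer changes. SAP 4.11 repeats the scheme: "The proportion of participants who are negative for ADA at baseline with a positive ADA result on study". Neither section defines baseline for ADA.

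The sampling schedules are Tables 9 to 11 in Protocol Appendix 2. All three mark ADA at screening (Day -56 to -1), Day 15, Day 29 and end of study, plus optional samples after an infusion reaction. The Day 1 pre-infusion row collects serum for PK and cytokines, but its ADA cells are blank. In Part 2, ADA is taken before the infusions on Days 15 and 29, so only the first infusion lacks a same-day sample.

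For people previously exposed to either drug, footnote b of Tables 10 and 11 (Parts 1B and 2) tells sites to "obtain screening samples for ADA (MGD014 and MGD020) at least 21 days prior to enrollment to allow for results to be reported before enrollment". Table 9 (Part 1A) has no such footnote.

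Re-entry is allowed. Protocol 4.1.2 states: "Participants who completed Part 1A may be considered for enrollment in Part 1B", on condition that they had no DLT and have no detectable ADA when they finish Part 1A. Protocol 4.1.3 has the matching rule for Part 2. Exclusions 20 and 21 (Protocol 5.2) bar previously exposed people who are ADA-positive to the relevant drug.

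**The concern.** A single screening sample serves two purposes. For eligibility it has to be early, so that the result is back before enrollment. For analysis the baseline should be as close to the first dose as possible, because it separates what was already present from what appeared under the new regimen. Footnote b meets the first need at the expense of the second, and does so in the one group with a documented reason to develop ADA before Day 1: people who have already received one of these drugs.

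Such a person could be negative at screening, convert because of the earlier dose, and be positive by Day 15. The plan would place that person in the group negative at baseline and positive on study. Someone already positive on Day 1 whose titer then rises would land there too, rather than among those positive at baseline with an increase. SAP 4.11 also allows the effect of immunogenicity on safety, PK and PD to be explored, so the classification may be carried into those summaries.

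**Working it through.** **Screening window.** Protocol 4.1: "The study consists of a screening phase of up to 8 weeks". 8 × 7 = 56 days, which agrees with Day -56 to -1 in the tables.

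**Interval from the baseline ADA sample to the first dose.** There is no Day 0, so a sample on Day -k is k days before Day 1.
- Any participant: 1 to 56 days.
- Previously exposed, Parts 1B and 2: 21 to 56 days. Enrollment falls within screening, so 21 days before enrollment is at least 21 days before dosing.

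**Interval to the first scheduled on-study ADA sample.** Day 15 is nominally 14 days after Day 1.
- Any participant: 1 + 14 = 15 to 56 + 14 = 70 days.
- Previously exposed: 21 + 14 = 35 to 56 + 14 = 70 days, of which 14 follow the new dose.

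With a Day 1 pre-infusion baseline, the unobserved pre-dose interval falls to about 0 days, and baseline to first on-study sample becomes 14 days.

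**What the entry conditions cover.** The conditions in Protocol 4.1.2 and 4.1.3 test ADA at the end of the earlier part. Exclusions 20 and 21 rest on the screening sample. Nothing scheduled tests ADA between that sample and the Day 1 infusion, so a conversion in that interval is invisible to both.

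**How late the interval falls after an earlier single dose.** Assume that the new screening sample follows completion of the earlier part (Day 43, nominally 42 days after the dose) and is taken at least 21 days before re-dosing. The new dose is then at least 42 + 21 = 63 days after the earlier one. Take the MGD014 half-life of 10 to 12.5 days (Protocol 2.3.2.1), a similar value for MGD020, and simple exponential decline:
- at 42 days, 0.5^(42/10) = 5% to 0.5^(42/12.5) = 10% of drug remains;
- at 63 days, 0.5^(63/10) = 1% to 0.5^(63/12.5) = 3% remains.

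The exposure driving a late conversion is therefore low, but not absent when the interval opens. These are fractions of drug remaining, not probabilities of conversion; the documents do not link the two.

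**Weight of one misclassified person.** With all dosed participants in the denominator: 1/3 = 33 points in a cohort of 3, 1/6 = 17 points in a cohort of 6 (the Part 2 maximum), and 1/18 = 5.6 points across a full Part 1B.

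**The case against.** The strongest reply is that the plan already screens out most of the risk. A Part 1 re-entrant has had ADA tests at Days 15, 29 and 43, must be negative on completing that part, and must be negative again at screening. Conversion would have to come after all of these, when little drug remains. If the 90-day rule on investigational therapy in exclusion 17 covers the earlier study dose, the separation is longer still. Whether it does is unclear, because exclusion 2 exempts MGD014 and MGD020 and exclusion 17 is silent. The endpoint is also descriptive, and on-study ADA enters neither the DLT definition nor the primary endpoint. All of this lowers the likelihood and the stakes. None of it supplies a result for the interval between screening and dose.

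Four stronger readings are tempting, and the documents do not support them.
- A reader might extend the problem to everyone. For never-exposed participants the documents give no reason for new ADA before dosing, and the 21-day rule is confined to Parts 1B and 2.
- A reader might infer that ADA incidence in Parts 1B and 2 is biased upward. The same conditions admit only re-exposed people without detectable ADA after an earlier dose, which could lower observed incidence. The net direction cannot be derived.
- A reader might take 21/35 = 60% to 56/70 = 80% as the share of carried-over conversions first seen at Day 15 that predate the new dose. That ratio assumes a constant conversion rate, for which the documents offer no basis.
- A reader might conclude that the loss is irreparable. Protocol 16.7 provides for retaining samples and, with consent, exploratory testing, so later ADA testing of Day 1 serum may be possible if volume and consent allow.

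**Conclusion.** The point holds for participants previously exposed to MGD014 or MGD020, chiefly in Parts 1B and 2. For them the default ADA baseline is 21 to 56 days old at dosing, and a conversion from the earlier exposure within that interval would be reported as arising on study. Both documents describe a positive result on study and do not call it induced by the regimen. Even so, this category is the natural source for the incidence endpoint and would ordinarily be read that way.

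The amount of misclassification cannot be stated, because neither the conversion rate nor the number of re-enrolled participants is given. What can be stated is the leverage: one person is 17 points in a cohort of 6. The conclusion assumes that screening is used as baseline, which is the only option the schedule leaves. This is an inexpensive improvement to a secondary descriptive endpoint and does not threaten the primary objective. A wording change alone would not be enough, because no scheduled Day 1 result exists to point to.

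**What to change.** 1. In Tables 9 to 11, add ADA to the existing Day 1 pre-infusion serum draw (MGD020 in all parts; MGD014 as well in Parts 1B and 2), at least for previously exposed participants.
2. In Protocol 14.5.2 and SAP 4.11, define the ADA baseline as the last sample before the first dose in that part: Day 1, or screening if Day 1 is missing.
3. Keep the screening sample, with its 21-day lead, for eligibility.
4. Show ADA results for previously exposed participants separately. This is needed in addition to the Day 1 sample, which cannot distinguish a late conversion from the earlier dose that appears after the new dose from one due to the new dose.

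The cost is one ADA assay per drug per participant. If applied to everyone at maximum enrollment, that is 30 × 1 + 18 × 2 + 6 × 2 = 78 assays, and fewer if limited to previously exposed people. Schedule and SAP wording also change. No visit or procedure is added; the laboratory should confirm that the serum volume is sufficient.

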14.5.3 Pharmacodynamic Analysis

Summary statistics for PD parameters listed in **Section 10.3** and changes from baseline will be summarized. Analyses may be presented graphically with possible associations between changes in PD measures of interest and study drug dose and exposure.

14.5.3.1 Serum Cytokines

Data will be tabulated and summarized by dose and time. Plots of serum cytokine levels versus time may be provided. Additional analyses may be conducted to characterize the relationship between study drug concentrations and serum cytokines (e.g., an exposure-response analysis), if deemed appropriate.

14.5.3.2 T-Cell Binding

Percentages of $CD4^+$ or $CD8^+$ cells in blood with bound MGD020 (Part 1A) or bound with both MGD020 and MGD014 (Part 1B and Part 2) will be calculated.

14.5.3.3 T-Cell Phenotype and Function

Percentages of $CD4^+$ or $CD8^+$ cells in blood with expression of markers of activation (e.g., CD25, CD69, CD134, CD137) or exhaustion (e.g., PD-1, LAG-3, TIM-3, TIGIT, CTLA-4) will be calculated.

14.5.3.4 Quantitative Viral Outgrowth Assay

In Part 2 only, for participants who complete the optional leukapheresis, changes in pre- and post-dose measurements of the frequency of resting $CD4^+$ T-cell infection by QVOA (2) will be

assessed. Data will be reported as infectious units per million (IUPM) and 95% CI values will be determined from the maximum likelihood method. Statistical significance of changes in QVOA values following dosing will be evaluated by a nonparametric 2-sided exact sign test. The exact sign test used for this analysis makes minimal statistical assumptions and is based solely upon whether IUPM values decrease following dosing. As QVOA is a robust and reproducible assay, declines of more than 50% in QVOA values from serial measurements are infrequently seen and would be suggestive evidence for HIV-1 reservoir depletion (11, 14).

14.5.3.5 Intact Proviral Deoxyribonucleic Acid Assay

In Parts 1A, 1B and 2, pre- and post-dose measurements of the frequencies of resting CD4+ T-cell infection by IPDA (4) will be analyzed. Data will be reported as intact HIV-1 provirus per million CD4+ T-cells. 95% CIs for IPDA values will be determined and the statistical significance of changes following dosing will be evaluated by a nonparametric 2-sided exact sign test. Like QVOA, declines of more than 50% in IPDA values from serial measurements would be suggestive evidence for HIV-1 reservoir depletion.

14.5.3.6 Resting CD4+ T-Cell-Associated HIV-1 gag RNA

In Part 2 only, changes in pre- and post-dose measurements of rca-RNA will be assessed. TATA binding protein RNA will be used as the reference to normalize HIV gene expression given its reported stability across treatment conditions (7). Data will be log-transformed and Wilcoxon Two-Sample test will be used for statistical analysis of rca-RNA of pre- and post-DART treatment as previously reported (13).

14.5.3.7 Plasma Viremia by Single Copy Assay

In Part 2 only, changes in pre- and post-dose measurements of levels of residual low-level HIV-1 viremia quantified by SCA will be assessed. Data will be reported as HIV-1 copies per mL plasma. 95% CIs for the SCA values will be determined and the statistical significance of changes following dosing will be evaluated by a nonparametric 2-sided exact sign test.

14.6 Efficacy Endpoints and Analyses

Not applicable.

14.7 Safety Endpoints and Analyses

14.7.1 Adverse Events

Treatment-emergent AEs will be summarized in tables and listings. All AEs prior to treatment (e.g., due to study-related procedures) will be presented in listings only. Tables will display the number and percent of participants that experience the given event.

AEs will be coded to the Medical Dictionary for Regulatory Activities (MedDRA) dictionary. AEs will be summarized by system organ class, preferred term, relationship to study drug, and highest severity.

14.7.2 Laboratory Values

Summaries of laboratory values will display descriptive statistics for numerically quantified laboratory assessments. Summaries will be grouped by laboratory panel (hematology, blood chemistry, and urinalysis) and will be displayed by study visit for each laboratory parameter. Shift tables may be produced.

14.7.3 Other Safety Endpoints

ECGs will be collected and analyzed. Vital signs will be summarized with descriptive statistics at each study visit and time point collected. Shift tables may be produced.

14.8 Other Assessments or Analyses

Any additional analyses will be defined in the statistical analysis plan.

14.9 Cohort Analyses and Monitoring

As described in **Section 4.2**, the decision to escalate doses from cohort to cohort will only occur based on consensus supporting escalation by the investigator (or designee) and medical monitor. The review will include aggregate safety data through the DLT period for all dosed participants from the prior dose cohort.

An independent safety monitor will receive monthly study progress and safety monitoring reports. Study feasibility and the achievement of study milestones will be assessed in these reports. Additionally, accrual, baseline characteristics, conduct of the study (including premature study discontinuations), any interruptions of ART, virologic failures, and all reported toxicities and events will be monitored during the study on a monthly basis. Safety data will be reviewed to assess the relationship of reported toxicities and AEs to study drug(s).

If at any time during the study, 2 or more participants (in any part of the study) experience a toxicity that is Grade 3 or higher and considered related to study drug (per investigator assessment) or 2 or more participants experience the same toxicity that is Grade 2 or higher and considered related to study drug (per investigator) then enrollment and further dosing of ongoing participants will be suspended and the independent safety monitor will be asked to review all safety data, review study drug attribution to the event(s), and recommend how the study should proceed with respect to resuming enrollment and continuing study drug.

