4.1.1 Part 1A: Single Ascending Dose of MGD020

Part 1A evaluates single ascending doses of MGD020 with a 1+3 design for cohorts 1–3 and a 3+3 design for cohorts 4–6. A 2-week DLT period is observed prior to escalation to the next cohort level.

Part 1A has 6 cohorts ([Table 1](#)). For cohorts 1–3, each cohort consists of 1 participant, unless a DLT occurs, which prompts expansion of the cohort to add an additional 3 participants. For cohorts 4–6, each cohort consists of 3 participants, with at least 24 hours between dosing of each participant within the cohort. If a DLT is experienced in 1 of the 3 participants in the cohort, the cohort will be expanded to add 3 additional participants. If one or more of the additional 3 participants treated at any given dose level also experiences a DLT, then that dose level will be defined as exceeding the MTD. The MTD will then be defined as the next lower dose level of MGD020. Escalation proceeds according to the rules described in [Section 4.2](#) until either the MTD or MAD is determined.

Table 1 **MGD020 Dose Escalation Scheme (Part 1A)**

Cohort	MGD020 Dose (mcg/kg)	Design
1	1	1+3
2	3	1+3
3	10	1+3
4	30	3+3
5	100	3+3
6	300	3+3

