4.1.3 Part 2: Multi-Dose Expansion Cohort: Fixed-Dose of MGD020 and Fixed-Dose of MGD014

Part 2 commences only after an MTD or MAD of MGD020 in combination with MGD014 has been determined in Part 1B. Part 2 is a multi-dose expansion cohort with sequential infusions of a fixed dose of MGD020 in combination with a fixed dose of MGD014 administered Q2W for 3 combination doses over 4 weeks (**Table 3**). MGD020 is dosed at the MTD/MAD determined in Part 1B (i.e., MTD_{1B}/MAD_{1B}). MGD014 is dosed at 300 mcg/kg, as determined from Study CP-MGD014-01.

Up to 6 participants may be enrolled in Part 2 using a conventional 3+3 design. If 2 or more participants in the cohort of 6 participants experience a DLT, enrollment and further dosing of ongoing participants will be suspended pending further assessment of safety data.

Table 3 MGD020 and MGD014 Combination Multi-Dose Expansion Cohort Scheme (Part 2)

Cohort	MGD020 ^a (mcg/kg)	MGD014 (mcg/kg)	Design
1	MGD020 MTD _{1B} /MAD _{1B}	300	3+3

- a The MGD020 dose is determined by the combination MTD or MAD in Part 1B.

Participants who completed Part 1 may be considered for enrollment in Part 2, provided they meet all eligibility criteria, did not experience DLT in Part 1, and do not have detectable ADA against MGD014 and/or MGD020 at the completion of Part 1.

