4.2 Dose Escalation Rules

Dose escalation from one dose cohort to the next higher dose cohort depends upon the clinical safety profile (e.g., evaluation of AEs, vital signs, ECGs, and clinical laboratory parameters) of the dose administered up to and including the preceding dose cohort. Dose escalation to the next dose level is permitted only after the participants enrolled in the current dose cohort have completed the DLT evaluation period and the safety data have been reviewed by the sponsor medical monitor and the study investigators. Evaluation of safety data from each cohort will include an assessment of the proportion of participants who receive planned doses, and the percentage of participants that require dose reductions or dose discontinuations for toxicity. Available data from participants both during and beyond the 2-week DLT evaluation period will be considered when making dose escalation decisions.

Dose escalation continues until all cohorts are enrolled, provided the MTD is not exceeded. If 2 or more of the participants in a dose cohort experience a DLT, the MTD will have been exceeded. If a DLT occurs in 1 participant in a dose cohort, the dose cohort will be expanded to an additional 3 participants. Prior to dosing any additional participants at the same dose, study drug safety and tolerability are evaluated over the entire 2-week DLT period for the first additional participant.

If the first additional participant does not experience a DLT during the DLT period, the 2 other additional participants can proceed to receive study drug at this dose with a minimum of 24 hours between dosing of each participant. If none of the 3 additional participants experience a DLT during the DLT period, dose escalation to the next dose cohort may proceed.

If any of the 3 additional participants experiences a DLT during the DLT period (≥ 2 DLTs within the same dose cohort), no further participants will receive a dose at this dose level, as the MTD will have been exceeded. Part 1B then proceeds at one dose level below the single-agent MTD_{1A}/MAD_{1A} of MGD020 determined in Part 1A. If only 1 participant was enrolled at the prior dose level in Part 1A, an additional 3 participants will be enrolled at the prior dose for evaluation of the MTD/MAD.

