4.3 Dose-Limiting Toxicity

DLT is defined based on treatment-related AEs that occur during the DLT period following study drug administration. The DLT period is defined as the period from initial infusion of study drug(s) through 2 weeks following the last study drug infusion.

Severity of AEs is graded according to the National Institute of Allergy and Infectious Diseases (NIAID) Division of Acquired Immunodeficiency Syndrome (DAIDS) Table for Grading the Severity of Adult and Pediatric Adverse Events, corrected version 2.1, July 2017 (see [Section 12.1.6](#)).

A DLT is any \geq Grade 2 treatment-related AE, with the following exceptions, based on the medical judgement of the investigator (or designee) and medical monitor:

- Grade 2 laboratory abnormality that lasts $<$ 72 hours and is not otherwise associated with clinical complications.
- Grade 2 fatigue that lasts $<$ 7 days.

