4.4.1 Dose Delays

Hold study drug administration for toxicity, pending assessment, management, and resolution of the AE. If the AE is assessed as unrelated to study drug(s) or does not meet DLT criteria, study drug(s) may be restarted at the previous dose and schedule, after appropriate recovery.

In Part 2, a dose delay of up to 7 days is allowed for drug-related or non-drug related AEs. Refer to [Section 7.1](#) for specific guidance on restarting study therapy after infusion reactions. A dose delay $>$ 7 days due to drug-related toxicity will prompt study drug discontinuation.

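### No rule pauses dosing of other participants, or calls an event-triggered independent review, after a single related Grade 4 or 5 event

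*Protocol*

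**What the plan says.** Section 14.9 holds the only study-wide suspension rule. It acts when "2 or more participants (in any part of the study) experience a toxicity that is Grade 3 or higher" and the event is considered related, or when two participants share the same related toxicity at Grade 2 or above. The count runs across all parts and the whole study. The monitor then reviews the data and recommends how to proceed.

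Section 4.1.3 (repeated in SAP Section 3.4) suspends Part 2 under this condition: "If 2 or more participants in the cohort of 6 participants experience a DLT".

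Section 4.3 puts the DLT floor at or above a "Grade 2 treatment-related AE, with the following exceptions" for some short-lived Grade 2 events. It has no higher tier. Section 4.2 then states: "If a DLT occurs in 1 participant in a dose cohort, the dose cohort will be expanded to an additional 3 participants". On pacing it adds: "Prior to dosing any additional participants at the same dose, study drug safety and tolerability are evaluated over the entire 2-week DLT period". That observation is of one added person; the other two follow if that person has no DLT.

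Spacing of the initial participants is set in Section 4.1.1 for Part 1A cohorts 4–6 ("each cohort consists of 3 participants, with at least 24 hours between dosing of each participant within the cohort") and in Section 4.1.2 for Part 1B ("with at least 72 hours between dosing of each participant within a cohort").

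Section 4.4.1 says "Hold study drug administration for toxicity, pending assessment, management, and resolution of the AE", and goes on to restarting at the same dose and schedule after recovery.

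**The concern.** The suspension rule depends on how many participants are affected and gives no extra weight to the worst grades. A first related Grade 4 or 5 event counts as one of the two that Section 14.9 needs, and nothing more. Within a Part 1 dose cohort it has the same consequence as a Grade 2 DLT: more people are dosed at that level.

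This is the first human exposure to MGD020 (Section 2.3.1.1), in virologically suppressed people who are told to expect no direct benefit (Section 2.5.2). Infusion reactions and cytokine release are named risks (Section 2.5.1). The study runs at 3–5 institutions, so a written halt also helps all sites to act alike on the same day. What is at stake is further exposure at a dose that has just produced a life-threatening or fatal related event, with the decision to pause left to discretion.

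**Working it through.** **1. What each rule does for the other participants**

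| Event | Section | Consequence for others |
|---|---|---|
| Two participants, related Grade 3+ | 14.9 | Suspension and independent review |
| Two participants, same related toxicity, Grade 2+ | 14.9 | Suspension and independent review |
| Two DLTs in Part 2 | 4.1.3; SAP 3.4 | Suspension pending safety assessment |
| Two DLTs in one dose cohort | 4.2 | No more dosing at that level |
| One DLT, any grade from 2 to 5, in a Part 1 cohort | 4.2 | Three more people at the same dose |
| One related Grade 4/5 event after the Part 1 DLT period | none | Weighed in escalation; neither expansion nor suspension |
| Grade 4 infusion reaction | 7.1.3 | None; affected person stops |
| Toxicity hold or discontinuation | 4.4.1, 4.5 | None; affected person only |

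The smallest number of participants that triggers any suspension or ad hoc independent review is 2. The number of such rules triggered by one related Grade 4 or 5 event is 0.

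The sixth row arises because the DLT period ends 2 weeks after the last infusion (Section 4.3), while Part 1 follow-up runs to Day 43 (Appendix 1, Table 7).

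**2. How many more people can be dosed at that level**

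Suppose the first participant has the event, no second DLT occurs in the cohort, and no other participant's event completes a 14.9 pair.

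- Three-person cohort (Part 1A cohorts 4–6, Part 1B): 2 initial + 3 expansion = 5. Of these, 2 + 1 = 3 can be dosed before the first added participant's 2 weeks are complete.
- Part 1A cohorts 1–3: 0 initial + 3 expansion = 3. Of these, 1 can be dosed before those 2 weeks are complete.

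If the pacing sentence in 4.2 is read as also covering the remaining initial participants, the timing changes but the total of 5 does not.

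**3. What a single-event trigger would cost in halts**

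The planned maximum reproduces: 3 × (1 + 3) + 3 × (3 + 3) + 3 × 6 + 6 = 12 + 18 + 18 + 6 = 54. It is a sum of cohort ceilings, and one DLT path does not reach it: Part 1B Cohort −1 opens only if Cohort 1 exceeds the MTD, and Cohort 2 is then not reached. I therefore use a path with no expansions and no de-escalation, and Part 2 full:

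n = (3 × 1 + 3 × 3) + (2 × 3) + 6 = 12 + 6 + 6 = 24.

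The documents give no Grade 4/5 rate, so the per-participant probability p is an assumption. Events are taken as independent.

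- P(at least 1) = 1 − (1 − p)^24
- P(at least 2) = 1 − (1 − p)^24 − 24p(1 − p)^23

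| Assumed p | At least 1 (proposed trigger) | At least 2 (present threshold) |
|---|---|---|
| 0.5% | 0.113 | 0.006 |
| 1% | 0.214 | 0.024 |
| 2% | 0.384 | 0.083 |

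These count Grade 4/5 events only. The present rule also halts for pairs involving Grade 3 or same-type Grade 2 events, so the last column understates how often it acts. At p = 1% the added chance of a halt is at most 0.214 − 0.024 = 0.190.

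**The case against.** The strongest reply is that the framework is already conservative and that one such event would not go unnoticed:

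- The DLT floor is Grade 2, early cohorts have one participant, and the 14.9 count is cumulative across parts.
- Doses are spaced by 24 or 72 hours, the first added participant is watched for 2 weeks, and Part 1 monitoring is 12 hours (Section 6.5.1). Section 2.4.3 expects infusion reactions and cytokine release within 24 hours.
- SAEs reach the sponsor within 24 hours (Section 12.2.2). SUSARs go to regulators and investigators, and to the IRB as site policy requires (Section 12.2.1).
- The sponsor assigns every participant to a cohort and can stop the study (Sections 9.4 and 16.10).
- Related MGD014 events in 21 participants were all Grade 1 (Section 2.3.2.1).

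All of this stands, and it lowers the risk. None of it requires a pause or an ad hoc review. Escalation consensus governs the next dose level, and the 2-week check itself involves dosing another person.

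A reader might go further and infer that no independent review is required at all. Section 14.9 contradicts this: the monitor receives monthly safety reports covering all reported toxicities.

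A reader might also multiply five other Part 2 participants by three doses and conclude that 15 combination doses could pass unreviewed. The schedule does not support that. Each course runs from Day 1 to Day 29. Under the 4.2 stagger the last two participants start at least 2 weeks after the first added one, so their third doses fall about six weeks after that person's first, beyond at least one monthly report.

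Nor should halt rates be compared at 54 participants. Besides being unreachable on one path, near-full enrollment implies many DLTs, which would probably already have triggered 14.9.

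**Conclusion.** The concern holds in this form: the plan lacks an automatic pause and an event-triggered independent review after one related Grade 4 or 5 event. It does not lack independent oversight, and nothing suggests that the sponsor would in fact carry on dosing; intervention is likely but discretionary.

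Followed literally, the text allows up to 5 more people at the same dose in a three-person cohort, or up to 3 in Part 1A cohorts 1–3. These are upper bounds under the conditions stated in the working. At the planned pace of at most 54 participants in about 24 months (54 / 24 = 2.25 per month), five more would on average take about two months and so span monthly reports. Not all of these exposures are avoidable, since a review may recommend continuing. No probability of a further event is claimed.

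This is a design choice rather than a contradiction in the text. It should be changed because the gap is in participant safety and closing it is cheap. Confidence is medium.

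**What to change.** Add to Section 14.9: any single Grade 4 or 5 event considered related to study drug, in any part and at any time, suspends enrollment and further dosing pending ad hoc review by the independent safety monitor. An exception for an isolated, asymptomatic Grade 4 laboratory value not confirmed on repeat is reasonable.

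Add to Section 4.2: no further participant in that cohort, initial or expansion, is dosed until the review is recorded.

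State who decides on resumption, because 14.9 provides only for a recommendation. One option is the investigator and medical monitor, whose consensus 14.9 already requires for escalation.

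The cost is a short amendment that uses the existing monitor and suspension process, a short delay if such an event occurs, and more halts than now. Some halts will be for events judged only possibly related, since Section 12.1.5 counts these as related even when another explanation exists. The laboratory exception limits halts for isolated values.
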